12.2. Measure Items (NIH REQUIREMENTS HIGHLIGHTED IN YELLOW)

11.2.1. Contact Information

Patient	
Name:	Last, First, MI
Address:	Include Apt # if applicable
Zip Code (enter separately for NIH)	XXXXX
Phone 1 (cell):	(xxx) xxx-xxxx
Phone 2:	(xxx) xxx-xxxx
Email 1:	
Email 2:	
Preferred method of contact?	Phone, text, email
Emergency Contact 1	
Name:	Last, First, MI
Relationship:	(spouse, family, friend)
Address:	Include Apt # if applicable
Phone:	(xxx) xxx-xxxx
Email:	
Emergency Contact 2	
Name:	Last, First, MI
Relationship:	(spouse, family, friend)
Address:	Include Apt # if applicable
Phone:	(xxx) xxx-xxxx
Email:	

12.2.2. Referral source

How did you get referred to the Center for Addiction Science?	open-ended referral to be categorized later
---	---

12.2.3. Screening Questionnaire

	Inclusion	
1.	Presenting for their intake visit to the Center for Addiction Science for treatment of opioid use disorder	Yes / No If no: Exclude

2.	Access to a telephone	Yes / No If no: Exclude
3.	Eligible for receipt of buprenorphine-naloxone medication (e.g., Suboxone, Bunavail, Zubsolv)	Yes / No If no: Exclude
4.	Able to understand consent procedures	Yes / No If no: Exclude
Exclusion		
5.	Have a known contraindication to buprenorphine-naloxone medication treatment for opioid use disorder	Yes / No If yes: Exclude

12.2.4. Exclusion reason (if applicable)

Exclusion reason variable to be entered by staff for ease of access for DSMB report:	List number of reason for exclusion from above screener.
--	--

12.2.5. Demographics

Date of Birth	xx/xx/yyyy		
Age			
Sex at Birth	Male	Female	
Gender Identity	Male	Female	Other (enter what is said)
Race	White/Caucasian	Black/African American	Multiracial
	Asian	Alaskan Native	Pacific Islander
	Native American	Other (specify)	
Ethnicity	Non-hispanic	Hispanic	
Highest level of education	8th grade or less	9th through 11th grade	12th grade or GED
	Associate's degree	Vocational/trade school	Some college
	Bachelor's degree	Graduate degree	
	Less than \$10,000 per year	\$10,000 to \$19,999 per year	\$20,000 to \$29,999 per year

Annual household income	\$30,000 to \$39,999 per year	\$40,000 to \$49,999 per year	\$50,000 to \$59,999 per year
	\$60,000 to \$69,999 per year	\$70,000 to \$79,999 per year	\$80,000 to \$89,999 per year
	Over \$100,000 per year	Prefer not to answer	
Do you currently have a job?	No	Yes-part time	Yes-full time
Relationship Status	Single	Married	Divorced
	Widowed	Cohabiting	
What insurance do you use when you visit the Center for Addiction Science?	(open-ended write in?)		

12.2.6. Opioid Use Disorder Criteria

Diagnostic and Statistical Manual of Mental Disorders - 5

Check all that apply:

1.	Are you often taking opioids in larger amounts or over a longer period of time than intended?	
2.	Have you tried or been unable to cut down or control your opioid use?	
3.	Have you spent a great deal of time in activities that are necessary to obtain your opioid, use the opioid, or recover from its effects?	
4.	Do you have cravings, or a strong desire to use opioids?	
5.	Is your opioid use resulting in failure to fulfill your role obligations at work, school or home?	
6.	Have you continued to use opioids despite having persistent or recurrent social or interpersonal problems (caused or exacerbated by the effects of opioids)?	
7.	Have you given up or reduced time spent of important social, occupational or recreational activities because of your opioid use?	
8.	Have you used opioids in situations in which it is physically hazardous?	
9.	Have you continued your opioid use despite physical or psychological problems that are caused or made worse by opioids?	
10.	*Tolerance Do you need to use more and more opioids to achieve your high? or Do you get less of an effect from your opioid than you used to?	
11.	*Withdrawal	

	Do you feel withdrawal when you don't take opioids? or Do you take opioids to avoid feeling withdrawal?	
--	---	--

Have Filemaker autoscore:

Total Number Boxes Checked: _____

Severity designated: Mild: 2-3 symptoms. Moderate: 4-5 symptoms. Severe: 6 or more symptoms

12.2.7. Adherent for first follow up physician visit

Showed up for Center for Addiction Science appointment at scheduled day/time?	Yes / No
AND	
Had buprenorphine in urine screen (either at the visit or when urine specimen came back from lab)?	Yes / No
If both items answered “Yes” then adherent is affirmed through Filemaker calculation	

12.2.8. Adherent for second physician visit

Showed up for Center for Addiction Science appointment at scheduled day/time?	Yes / No
AND	
Had buprenorphine in urine screen (either at the visit or when urine specimen came back from lab)?	Yes / No
If both items answered “Yes” then adherent is affirmed through Filemaker calculation	

11.2.9. Adherent for third physician visit

Showed up for Center for Addiction Science appointment at scheduled day/time?	Yes / No
AND	
Had buprenorphine in urine screen (either at the visit or when urine specimen came back from lab)?	Yes / No
If both items answered “Yes” then adherent is affirmed through Filemaker calculation	

12.2.10. Adherent for fourth physician visit

Showed up for Center for Addiction Science appointment at scheduled day/time?	Yes / No
AND	
Had buprenorphine in urine screen (either at the visit or when urine specimen came back from lab)?	Yes / No
If both items answered "Yes" then adherent is affirmed through Filemaker calculation	

12.2.11. Cumulative Adherence

Number of treatment visits attended (allow for drop out, drop back in)	Filemaker calculation
--	-----------------------

11.2.12. Urine Toxicology

Check all that are present in urine collected by Center for Addiction Science		
Buprenorphine	Yes	No
THC	Yes	No
Cocaine	Yes	No
Opiates	Yes	No
Amphetamines	Yes	No
Methamphetamines	Yes	No
Phencyclidine (PCP)	Yes	No
MCMA	Yes	No
Barbiturates	Yes	No
Benzodiazepines	Yes	No
Methadone	Yes	No
Tricyclic antidepressants	Yes	No
Oxycodone	Yes	No
ETC	Yes	No
Fentanyl	Yes	No

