3.3. Design and Outcomes

This project will use a randomized design to compare treatment satisfaction and effectiveness of Contingency Management (CM) and Brief Motivational Intervention + Substance Free Activities Session + Mindfulness-Based Adherence Promotion (BSM) for medication adherence in patients who are initiating buprenorphine-naloxone treatment at our Center for Addiction Science (N=40). The interventions will take place across the first 4 physician visits of buprenorphine-naloxone treatment, starting after treatment intake.

Primary outcomes will include feasibility and satisfaction at the fourth weekly intervention visit, and an efficacy comparison of intervention group differences in buprenorphine-naloxone treatment adherence, defined as (1) attendance at physician visit AND (2) buprenorphine-naloxone presence in urine toxicology.

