3.6.2. Sessions 1-4: Intervention Treatment

- 1) Assessment questionnaires with interventionist
 - a) Assessment questionnaires completed (10 minutes)
- 2) Engage in either CM (2 minutes) or BSM (30 minutes)
 - a) BSM:
 - i) All BSM sessions will be audio-recorded in order for the study staff to evaluate treatment fidelity. Participants will be informed when the recording device is on, and permission to record will be obtained as soon as the recording device is started. Participants may refuse to have the session recorded and still participate. Audio recordings will be de-identified and labeled with a Study ID number stored on an encrypted computer.
 - b) CM:
 - i) A number wheel (pickerwheel.com) with varying levels of gift cards (ranging from \$25 to \$100) will be available.
 - ii) Urine toxicology will be obtained from the chart to assess presence of buprenorphine in urine (criteria for reward).
 - iii) Participants will be informed of the buprenorphine toxicology result.
 - (1) **IMPORTANT: IT IS BUPRENORPHINE IN URINE THAT RESULTS IN A GIFT CARD WIN.**
 - (2) **We ARE NOT providing feedback to the participant about the use of illicit substance presence in urine as this is not criteria for reward.**
- 3) Chart Review Following Intervention

- a) Information about buprenorphine-naloxone dose, all urine screen results (13 panel), and other substance use disorder diagnosis will be copied from the participant's medical chart.
- b) Opioid prescriptions will be obtained from prescription drug monitoring database.

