12.2.22. Prescription Drug Monitoring data

Number of opioid prescriptions found in the prescription drug monitoring database since last visit	#
--	---

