Statistical Analysis Plan: SMART Project 3 (Efficacy Study)

Because these analyses will focus on determining and intervention feasibility and satisfaction, and preliminary intervention effect sizes (with less concern focused on testing for statistical significance), outcome analyses will be conducted using a separate analysis for each outcome at each follow up observation. To compare groups, baseline and follow up variables will be entered into a 5 (baseline vs. follow ups at 1, 2, 3, and 4 weeks) by 2 (CM vs. BSM) analysis of variance (ANOVA) which will yield effect sizes for time, and interactions of time by intervention. The primary dependent variables will be attendance at physician visits, saliva drug screen data (positive for buprenorphine and negative for illicit opioids), and prescription drug monitoring. We hypothesize that a greater number of CM participants will demonstrate adherence to buprenorphine-naloxone than BSM, but that those randomized to BSM will report increased time allocated to substance-free activities, decreased delayed reward discounting, and demand for opioid.

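### The urine form has more rows than the 13-panel screen and no code for an untested row, and prescriptions are kept only as a count, so the SAP's illicit-opioid-negative variable cannot be reliably derived

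*Protocol*

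**What the plan says.** - **Source of the urine result.** Protocol section 3.6.2 has staff copy "all urine screen results (13 panel" from the chart after each session. The 13 analytes are not listed anywhere.
- **Receiving form.** Section 11.2.12 is headed "Check all that are present in urine collected by Center for Addiction Science". It has 15 rows, each answered Yes or No: buprenorphine through oxycodone, then ETC, then fentanyl. There is no answer for a substance that was not tested or a visit without a specimen.
- **Prescriptions.** Section 3.6.2 says "Opioid prescriptions will be obtained from prescription drug monitoring database". The only field for this, in section 12.2.22, is "Number of opioid prescriptions found in the prescription drug monitoring database since last visit", answered with one number. Neither place says whether buprenorphine counts as an opioid here.
- **Use in the analysis.** The SAP lists among its primary dependent variables "saliva drug screen data (positive for buprenorphine and negative for illicit opioids". It gives no rule for deriving this variable.
- **The protocol's own outcome.** Section 3.3 defines adherence by "1) attendance at physician visit AND (2) buprenorphine-naloxone presence in urine toxicology", with no illicit-opioid component.

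**The concern.** One of the SAP's primary variables needs two facts about every screen: whether each opioid was tested and absent, and, if an opioid was present, whether it had been prescribed. The forms do not reliably keep either fact. Under a heading that asks staff to mark what is present, an analyte that was never tested may end up looking the same as one tested and not found. An opiate, oxycodone or methadone result may come from a prescription, and a bare count does not show which drug was prescribed or when.

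The comparison between arms makes this more than a matter of tidiness. Section 3.6.2 makes the CM reward depend on buprenorphine alone, whatever else the urine shows. Opioid use alongside buprenorphine is therefore one place where the arms could plausibly differ. If untested rows are read as negative, part of such a difference could be lost. The documents do not show that such a difference exists.

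**Working it through.** **1. Row count.** The plan's figure is 13 (section 3.6.2).

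| Rows counted on the form in 11.2.12 | Number |
|---|---|
| All rows | 15 |
| Without ETC | 14 |
| Without ETC and fentanyl | 13 |

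The figure of 13 is matched exactly if ETC and fentanyl both lie outside the panel, but the documents do not say so. What follows without assumption is 14 − 13 = 1: at least one named row is not on the panel. If ETC is itself an analyte, 15 − 13 = 2 rows are not. Fentanyl is a candidate because it is listed after the first 13 rows.

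**2. States against codes.** A row can be in four states: detected, tested and not detected, not tested, or no specimen. The form has two answers. The last state is foreseeable, because section 8.6 continues assessments after a participant leaves clinic treatment. The completeness check in section 8.8.1 may catch a blank, but it supplies no code to put there.

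**3. Which records can be classed.** Besides buprenorphine, the form has four opioid rows: opiates, methadone, oxycodone and fentanyl. Cross the first three (present or absent), fentanyl status, and prescription count (zero or above zero).

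| | All four rows tested | Fentanyl may also be untested |
|---|---|---|
| Patterns | 2³ × 2 × 2 = 32 | 2³ × 3 × 2 = 48 |
| Negative | 2 | 2 |
| Positive, count zero: non-prescribed | 15 | 22 |
| Positive, count above zero: unresolved | 15 | 22 |
| Other rows negative, fentanyl untested: unresolved | 0 | 2 |

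These are patterns, not probabilities. Classing a positive with count zero as non-prescribed assumes that the count is complete and that nothing filled before the last visit was still being taken. If buprenorphine is counted, a zero will be rare in treated patients, and most positives fall in the unresolved row.

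**4. Possible size of the fentanyl error.** The documents give no rates, so both inputs are assumptions. Let u be the share of otherwise opioid-negative screens without a fentanyl test, and q the share of those screens with fentanyl-only use, with testing unrelated to use. If untested is read as negative, the false-negative share is u × q.

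| u | q = 5% | q = 10% | q = 20% | q = 30% |
|---|---|---|---|---|
| 0% | 0% | 0% | 0% | 0% |
| 25% | 1.3% | 2.5% | 5% | 7.5% |
| 50% | 2.5% | 5% | 10% | 15% |
| 100% | 5% | 10% | 20% | 30% |

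For scale, 40 participants × 4 sessions = 160 planned session screens, or 80 per arm.

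**5. Specimen.** The SAP names saliva. The list of measures (section 12.1) contains urine toxicology and no saliva test. As the protocol stands, the form in 11.2.12 is the only toxicology source for the SAP variable.

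**The case against.** The strongest reply is that the forms may work in practice.

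- **Fentanyl may be tested.** It has its own row, which suggests results were expected. The adherence forms foresee a later laboratory result ("Had buprenorphine in urine screen (either at the visit or when urine specimen came back from lab"), so more than one source may exist. With separate Yes and No cells, an untested row could be left blank. A reader might infer from the row count that fentanyl is off the panel and that untested fentanyl is stored as negative; the documents state neither. What remains is that the form cannot show whether a test was done. The laboratory provision is written for buprenorphine and does not say whether fentanyl is tested.
- **Much of the variable can be derived.** A record with all opioid rows tested and negative needs no prescription data. A positive with a complete count of zero can also be classed. The timeline followback (section 12.2.13) asks day by day about non-prescribed opioids, heroin, fentanyl and methadone. All this stands, and a reader who concludes that the variable cannot be derived at all goes too far. Self-report is nevertheless a cross-check, not the drug-screen result that the SAP names.
- **The prescription count may not be meant for this.** The SAP lists prescription monitoring as a separate variable, and nothing says it decides urine positives. That is correct. But without drug and date there is no other prescription detail on the listed forms with which to separate a prescribed opiate, oxycodone or methadone positive from an illicit one.

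**Conclusion.** The concern holds for the SAP's drug-screen variable: as the forms are written, it cannot be reliably derived. Two groups of records fail: those with an untested opioid row or no specimen, and those with an opioid positive and a prescription count above zero. The row mismatch (14 named rows against 13), the missing codes and the bare count are on the face of the protocol and need no assumption.

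The size is unknown. The fentanyl error is 0% if every opioid row is tested, and reaches 30% only at the extreme of the assumed ranges. Which analyte is off the panel is not stated.

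A reader might also infer that the trial's adherence result is compromised. It is not: attendance plus buprenorphine in urine uses neither the other opioid rows nor the prescription count.

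**What to change.** 1. **Panel.** List the 13 analytes, say what ETC means, and state the source of any row outside the panel.
2. **Section 11.2.12.** Replace Yes/No with Positive, Negative, Not tested and No specimen for each row.
3. **Section 12.2.22.** Record drug name, fill date and days' supply for each opioid entry, and keep buprenorphine separate from other opioids.
4. **SAP specimen.** Correct saliva to urine, so that the variable matches what is collected.
5. **SAP derivation.** Derive illicit-opioid negativity from the opioid rows actually tested, and say how a positive with a matching active prescription is handled. A match does not exclude non-prescribed use of the same class. Report by arm the number of records with fentanyl untested. Add a sensitivity result limited to records with fentanyl tested, and use the timeline followback as a cross-check.

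Setting every record without a fentanyl test to missing is not advised: if fentanyl is off the panel, that rule would empty the variable.

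The cost is a change of answer options, a few more fields from a database that staff already open, and a short SAP paragraph. No new test is needed. Some records will become undetermined. If tested status is not captured at abstraction, recovering it later means reopening the charts.

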12.2.13. Timeline followback

Today's date:							
	(fill in day of the week)						
	(example) Monday	(example) Tuesday	(example) Wednesday	(example) Thursday	(example) Friday	(example) Saturday	(example) Sunday
Did you have any illicit substances or	Yes / No						

alcohol on   day?							
If yes to alcohol: Number of standard drinks on this day?	# drinks						
Marijuana on this day?	Yes / No						
Cocaine on this day?	Yes / No						
Crack on this day?	Yes / No						
Amphetamine or other stimulant on this day?	Yes / No						
Opioid drugs that weren't prescribed to you? (not including fentanyl or methadone)	Yes / No						
Heroin on this day?	Yes / No						
Hallucinogens, including MDMA/ecstasy on this day?	Yes / No						
Sedatives and hypnotics, excluding Benzodiazepines on this day?	Yes / No						
Benzodiazepines on this day?	Yes / No						
Inhalants on this day?	Yes / No						
Fentanyl on this day?	Yes / No						
Methadone on this day?	Yes / No						

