8.2. Enrollment

8.2.1. Consent

Project staff will answer any questions about the entire process and an informed consent will be obtained. No study assessment will take place prior to obtaining consent from each subject. Standard language in our consent form assures the participants of the confidential nature of the study and the ability to withdraw from the study at any time. The consent forms will contain HIPAA language. This study will be approved by the UTHSC IRB.

Participants will be given a copy of the consent statement for their records. The consent discussion will be documented on the eligibility page of the FileMaker Database.

Participants will be informed that regardless of their adherence to clinic visits or use of buprenorphine-naloxone (the primary study outcome), they will be eligible to complete assessments at scheduled intervals and will be compensated for these assessments. This will enable the study team to discover whether drop out of treatment leads to relapse to opioids and if treatment is sought elsewhere.

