12. MEASURES

12.1. Table 1. List of Measures

Measure	Time to Complete (minutes)	Baseline	1,2, 4, and 8 week sessions	8 week blind	Medical Chart at 30 days
Contact Information	1	X			
Referral source (how did they get to the CAS)?	<1	X			
Screening Questionnaire	<1	X			
Exclusion reason (if applicable)	n/a				
Demographics (gender/race/ethnicity/education/zip code/insurance)	3	X			
Opioid Use Disorder (Diagnostic and Statistical Manual of Mental Disorders-5) ⁹³ interview	1	X			
Attended first physician visit	n/a		X		
Attended second physician visit	n/a		X		
Attended third physician visit	n/a		X		
Attended fourth physician visit	n/a		X		
Number of treatment visits attended (allow for drop out, drop back in): CUMULATIVE ADHERENCE	n/a				X
Urine Toxicology (buprenorphine and all other substances)	n/a	X	X		X
Timeline followback on alcohol, substance use, and opioid use	3	X	X		
Delay Discounting ⁵⁸	2	X		X	
Opioid Purchase Task ⁴⁶	1	X	X		
Engagement in Substance Free Activities ⁵⁴	2	X		X	
Time Spent On Activities	2	X			
Opioid Craving Symptoms ⁹⁵ (Opioid Cravings Scale)	1	X	X		
Buprenorphine-Naloxone dose log (did you miss any days?)	<1		X		
Dosage of Buprenorphine-Naloxone Prescribed (obtained from medical record at each session)	n/a	X	X		X
Treatment Satisfaction	4			X	
Prescription Drug Monitoring data	n/a	X	X		X
PEG for Chronic pain (3 items)	<1	X	X		
EQ5D5L (6 items) Quality of life for cost-effectiveness analyses	3	X		X	
PHQ-2 depression 2 items	<1	X	X		
GAD 2 anxiety 2 items only (also a 7 item version)	<1	X	X		
Treatment history (times in treatment, medication used)	<1	X			
Economy Contribution (3 items)	<1	X	X		
If dropped out: Are you receiving but (or opioid replacement) treatment somewhere else?	<1		X		
Adverse Events	<1		X		
Participant time to complete all measures at sessions:		20.5	11	10	n/a

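### The timeline followback limits only the general opioid row to non-prescribed drugs, so its daily data cannot separate methadone treatment from street methadone in drop-outs

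*Protocol*

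**What the plan says.** The grid in Protocol 12.2.13 has seven day columns and a Yes/No answer for each drug. It opens with "Did you have any illicit substances or" alcohol on the day in question, followed by a drinks count that is explicitly conditional on alcohol. The drug rows carry no condition.

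The general opioid row reads "Opioid drugs that weren't prescribed to you? (not including fentanyl or methadone"). The drugs it sets aside appear further down as "Fentanyl on this day" and "Methadone on this day". Neither row mentions prescription. The same is true of "Benzodiazepines on this day", "Amphetamine or other stimulant on this day" and the sedative row.

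Protocol 8.2.1 and 8.6 (Intervention Sessions) keep people in assessment after they leave clinic treatment. Section 8.2.1 gives the reason: to "discover whether drop out of treatment leads to relapse to opioids and if treatment is sought elsewhere". Table 1 (12.1) lists a matching item: "If dropped out: Are you receiving but (or opioid replacement) treatment somewhere else". The form itself, 12.2.29, has two Yes/No questions: one on buprenorphine-naloxone from another provider, and one on any current treatment for opioid use disorder.

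The SAP takes its illicit-opioid variable from a drug screen. It does not name the followback.

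**The concern.** Section 8.2.1 wants two things learned about people who leave: whether they relapse, and whether they are treated elsewhere. A Yes in the methadone row fits either answer. The two routes to treatment elsewhere are also handled in opposite ways. A person prescribed buprenorphine by another provider can truthfully answer No in the general opioid row. A person dispensed methadone by a program would answer Yes in the methadone row, if it is asked as written.

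The followback carries unusual weight for these people. The urine toxicology form (headed 11.2.12) covers urine collected by the clinic, and the results are copied from the clinic chart (3.6.2), so someone who no longer attends supplies no new clinic urine. Of the measures in Table 1, the followback is then the only day-by-day record of opioid use. If the source of the methadone is not asked at the time, it cannot be rebuilt reliably afterwards.

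**Working it through.** The documents give no figure to reproduce. The check compares the wording of the items, then bounds the possible effect.

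**1. Which rows separate prescribed from other use?**

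| Row in 12.2.13 | Limited to non-prescribed use? |
|---|---|
| General opioids (fentanyl and methadone excluded) | Yes |
| Methadone | No |
| Fentanyl | No |
| Benzodiazepines | No |
| Other sedatives and hypnotics | No |
| Amphetamine or other stimulant | No |

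**2. Does the opening row supply the missing limit?** The form does not say. Two features suggest that its authors did not rely on it. A condition is written out where one is wanted (the drinks count). And if the opening row already removed prescribed drugs, the limit in the general opioid row would be unnecessary. Even as a gate, it opens on any day with alcohol or an illicit drug, and the methadone row is then asked without a limit.

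**3. Can other items recover the distinction?**
- 12.2.29: No to buprenorphine-naloxone elsewhere, Yes to any treatment, and daily methadone in the grid together suggest a methadone transfer. But any treatment could be counseling, methadone is not named, and there is no start date with which to reclassify single days.
- Table 1 describes the item as covering opioid replacement. The form's two questions do not use that term.
- 12.2.22 (prescription monitoring) holds a count of opioid prescriptions, with no drug name.

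**4. Size.** Inputs from the documents: 7 day columns (12.2.13) and 20 participants per arm (3.5). Assumptions: (a) the person takes treatment methadone every day; (b) there is no other opioid use; (c) the methadone row is asked on *d* of the 7 days; (d) a methadone Yes is counted as an opioid-use day.

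- Days counted = *d*. Days counted if the row were limited to non-prescribed use = 0. Difference = *d* days per week.
- Shift in the mean of an arm of 20, per such person = *d*/20.

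| Situation | *d* | Shift in arm mean (days/week) |
|---|---|---|
| No gate | 7 | 7/20 = 0.35 |
| Gate, with alcohol or illicit non-opioid use on 2 days (illustrative) | 2 | 2/20 = 0.10 |
| Gate, no other use | 0 | 0 |

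If assumption (d) fails, the shift is 0 in every row.

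**5. Why no percentage of drop-outs is given.** Let *n* be the number of drop-outs, *t* the number who transfer to methadone, and *r* the relapse rate among the rest. The counted share minus the true share is [(*n* − *t*)*r* + *t*]/*n* − (*n* − *t*)*r*/*n* = *t*/*n*. The result is simply the assumed transfer rate, and the documents give none.

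**The case against.** The strongest reply is that the form records methadone, not relapse. Methadone has its own row, so those days stay identifiable. Neither document pools that row into opioid use or defines relapse from the followback. This stands. A reader might infer that a person who moves to methadone treatment is recorded as using opioids every day; the documents do not support that. They support only that such a person could be counted so, because no scoring rule is written.

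Second, an interventionist conducts the session assessments, so the illicit-or-alcohol framing may well be conveyed to the participant. Under that reading a transfer patient with no other use scores 0 of 7. This also stands as a possibility, and it is why the range starts at zero. It does not settle the point, because the form leaves the reading to whoever administers it.

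Third, 12.2.29 already captures treatment elsewhere. That is partly right: it flags probable transfers, but without the medication or the dates.

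Fourth, no main result depends on this. Primary outcomes in Protocol 3.3 are feasibility, satisfaction and adherence; the SAP's primary variables are visit attendance, the drug screen and prescription monitoring. This stands in full. A reader might also infer that the arm with more transfers would look worse. No comparison of relapse between arms among drop-outs is planned, so that inference has no analysis behind it.

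Finally, the benzodiazepine, sedative and stimulant rows have no bearing on opioid relapse. They are mentioned only for consistent wording.

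**Conclusion.** The concern holds as a measurement weakness of limited reach. The followback applies the non-prescribed limit to one opioid row and omits it from methadone and fentanyl, and it leaves the status of the opening row open. For drop-outs, the daily data alone cannot tell methadone treatment from street methadone, and 12.2.29 repairs this only in part. The aim stated in 8.2.1 is weakened; no SAP primary variable is affected.

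The effect lies between 0 and 7 days per week per affected person, or 0 to 0.35 days in the mean of an arm of 20. The upper end requires daily treatment methadone, no gate, no other opioid use, and a decision to count methadone as opioid use. The number of people affected is unknown. With 20 per arm, drop-outs will be few in absolute terms, so even one or two ambiguous records could matter to a description of what happens after drop-out.

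**What to change.** - In 12.2.13, add *that was not prescribed or dispensed to you* to the methadone and fentanyl rows and, for consistency, to the benzodiazepine, sedative and stimulant rows.
- State on the form whether the opening row is a gate for the drug rows.
- Add one row to the grid, or a field to 12.2.29, recording methadone or buprenorphine received from a treatment program. A daily row, or a start date with the 12.2.29 field, would allow single days to be classified.
- In the SAP, define how the followback rows form an opioid-use day, and state that days with only prescribed or program-dispensed medication do not count.

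The cost is a slightly longer form and no added visit. Records already collected keep the old wording and can be only partly reclassified from 12.2.29; they should be marked as such in any report of use after drop-out.
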